Participants will be asked to check glucose from CGM at 2am each morning before their treatment visit. If the CGM value is above 150 mg/dl, participants will be asked to take 80% of the correction bolus. If the glucose is less than 100 mg/dL they will be instructed to take 15 grams of carbohydrate. The participant will be asked to check his/her glucose before driving to the clinic and to bring a snack in the car in case hypoglycemia does occur (in which case, the participant must park and treat the hypoglycemia). After the first treatment visit, the washout period will be at least 3 days calculated from the day of admission until the start of the next admission. After arrival, women of childbearing potential will receive a urine pregnancy test if the last pregnancy test was more than 7 days prior. This test must be negative before further participation is allowed.

An assessment will take place at the beginning of each of the participant's closed-loop studies. We will inquire whether the participant has had changes in their medications and/or medical history to confirm the participant hasn't developed any study exclusion criteria. A CBG will be obtained and measured by a Contour Next glucose meter. When they arrive, participants will be given 15 grams of oral carbohydrate if the CBG reading is less than 70 mg/dl. CBG values > 300 mg/dl will be managed at the discretion of the investigator with a correction bolus and serum ketones will be checked. If serum ketones are >0.6 mM, the study will not be started and insulin therapy will be guided by the onsite investigator. The order of the visits will be randomized.

An Omnipod will be filled with aspart insulin. We will use only name brand insulin, not generic insulin. The Omnipod will be primed and inserted into the skin of the participant's abdomen or flank as directed by the manufacturer through the iPancreas smart phone application on a provided study phone. If applicable, participants will disconnect his/her own pump and remove his/her own insulin infusion set once insulin delivery has started via the Omnipod. If, applicable for participants on multiple daily injection therapy at baseline, we will verify time of last long

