Meal detection will be enabled for the study. If iPancreas does not auto-detect the meal after 30 minutes of when they start eating, the study coordinator will assist the participant to enter a meal with a reduction to the amount of carbs entered based on the amount of time since the meal occurred, at the investigator's discretion. Participants will complete a pictorial nausea rating scale for reported nausea at study start and at approximately 6 hours after the first and second meal to report the worse nausea/vomiting they experienced over the prior 6 hours (the Baxter Retching Faces [BARF] scale) (see Protocol Appendix D)[78] and the approximate duration of the nausea.

The MPC closed loop system with the meal detection algorithm can detect if a meal has been eaten, estimate the grams of carbohydrates consumed then dose an insulin bolus based on the estimated grams of carbs, user's carb ratio and estimated time since the meal was consumed. The bolus is delivered automatically. The system reduces the bolus (per calculation below) by 25% as the detection occurs on average 25 minutes after meal is consumed.

$$Bolus(units) = \frac{\text{estimated carbohydrates (g)}}{\text{carb ratio } (\frac{g}{unit})}$$

If CBG >300mg/dL before the lunch meal, then the study will be stopped early and the participant will be given the option to return on a different day for the second meal.

The meal detection algorithm can be enabled or disabled through the insulin profile settings for a given time period. In order to avoid a meal detection before the two scheduled meals, the meal detection algorithm will be disabled through the insulin profile in between the meals.

If stopping criteria for hyperglycemia is reached, the study investigator will calculate a meal bolus with correction dose as in the equation below if no meal bolus was given by the system, otherwise, the investigator will calculate a correction bolus based on current glucose, target

glucose, and correction factor. The final dose that is delivered to the participant will be adjusted if needed by a study investigator considering insulin-on-board, time since meal consumption, and CGM trend. The Omnipod site will be assessed to determine if the insulin should be delivered via the Omnipod, syringe, or via the participant's own insulin pump after it is reconnected.

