$$\text{Total Insulin Bolus} = \frac{\text{Carbohydrate (g)}}{\text{Carbohydrate Ratio}} + \frac{\text{Current glucose} - \text{Target Glucose}}{\text{Correction Factor}} - \text{IOB}$$

Discharge from inpatient clinic

The study will be terminated and the participant's own insulin pump or home basal insulin will be restarted. The study investigator will consult with the participant regarding appropriate insulin dosing for the remainder of the day. The Polar watch and Omnipod will be removed from the participant. The participant will wear Dexcom sensor until just prior to discharge to track the glucose and trend arrow. Participants will complete a pictorial nausea rating scale (the Baxter Retching Faces [BARF] scale), if applicable (see Protocol Appendix D)[78]. All infusion and sensor sites will be inspected for signs of irritation or infection. In addition, the sensor will be inspected for the possibility of breakage or fracture. If there is any evidence of sensor breakage, it will be recorded. If an area of inflammation of 1 cm or greater exists around the point of insertion, a de-identified photograph will be taken of the area and the participant will return 1-3 days later for a follow-up visit. A capillary blood glucose value will be measured. Participants will be given oral carbohydrate for values below 85 mg/dL, and if capillary blood glucose is greater than 180mg/dL, participants will be instructed to take a correction bolus from their home insulin pump or via home insulin pen/vial per their usual home settings after reviewing this dose with the study investigator who will modify dose if needed considering current insulin on board. The participant can then be discharged home if the next capillary blood glucose measurement 30 minutes later is less than 300 mg/dL or if the CGM glucose trend arrow shows flat arrow (increasing/decreasing less than 1 mg/dL each minute) or a down arrow (decreasing >30mg/dL in 30 minutes).

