An assessment will take place at the beginning of each of the participant's closed-loop studies. We will inquire whether the participant has had changes in their medications and/or medical history to confirm the participant hasn't developed any study exclusion criteria. A CBG will be obtained and measured by a Contour Next glucose meter. When they arrive, participants will be given 15 grams of oral carbohydrate if the CBG reading is less than 70 mg/dl. CBG values > 300 mg/dl will be managed at the discretion of the investigator with a correction bolus and serum ketones will be checked. If serum ketones are >0.6 mM, the study will not be started and insulin therapy will be guided by the onsite investigator. The order of the visits will be randomized.

An Omnipod will be filled with aspart insulin. We will use only name brand insulin, not generic insulin. Additionally, a second Omnipod will be filled with Pramlintide (Symlin, AstraZeneca). The iPancreas system will deliver pramlintide in a fixed ratio to insulin at 6 mcg of pramlintide delivered for every 1 unit of insulin. The Omnipod(s) will be primed and inserted into the skin of the participant's abdomen or flank as directed by the manufacturer. The pods will be placed at least 4 inches apart. If applicable, participants will disconnect his/her own pump and remove his/her own insulin infusion set once insulin delivery has started via the Omnipod(s). If, applicable for participants on multiple daily injection therapy at baseline, we will verify time of last long basal insulin administration. Participants will wear a Polar M600 fitness watch to inform the controller about physical activity. The research staff will initialize the system, input insulin settings and begin the closed-loop study. Two staff will review each of the settings to confirm the settings are entered correctly. Participants will receive training on using the iPancreas smart phone application. A member of the study staff will remain near to the participant for the duration of the study to address any alerts or issues that arise. The study investigator will be on call for the duration of the study.

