The study will be terminated and the participant's own insulin pump or home basal insulin will be restarted. The study investigator will consult with the participant regarding appropriate insulin dosing for the remainder of the day, considering pramlintide on board as tracked by the iPancreas system. If this level is elevated,, the participants will be offered an additional meal to eat before they discharge. The study investigator will consult with the participant in regards to a safe mealtime insulin dose given from their home pump or insulin pen.

The Polar watch and Omnipods will be removed from the participant. The participants will wear Dexcom sensor until just prior to discharge to track the glucose and trend arrow. Participants will complete a pictorial nausea rating scale (the Baxter Retching Faces [BARF] scale), if applicable (see Protocol Appendix D)[78]. All infusion and sensor sites will be inspected for signs of irritation or infection. In addition, the sensor will be inspected for the possibility of breakage or fracture. If there is any evidence of sensor breakage, it will be recorded. If an area of inflammation of 1 cm or greater exists around the point of insertion, a de-identified photograph will be taken of the area and the participant will return 1-3 days later for a follow-up visit. A capillary blood glucose value will be measured. Participants will be given oral carbohydrate for values below 85 mg/dl with a repeat capillary blood glucose every 15 minutes until glucose is \geq 85 mg/dL. If capillary blood glucose is greater than 180mg/dL, participants will be instructed to take a correction bolus from their home insulin pump or via home insulin pen/vial per their usual home settings after reviewing this dose with the study investigator who will modify dose if needed considering current insulin on board.

If the initial capillary blood glucose was > 85 mg/dL, the participant can then be discharged home if the next capillary blood glucose measurement 30 minutes later is less than 300 mg/dL or if the CGM glucose trend arrow shows flat arrow (increasing/decreasing less than 1 mg/dL each minute) or a down arrow (decreasing >30 mg/dL in 30 minutes). If the initial capillary blood glucose was < 85 mg/dL, then the participant will be given oral carbohydrates and we will repeat a fingerstick every 15 minutes until glucose is ≥ 85 mg/dL and the CGM trend arrow is flat or trending up, then patient can be discharged.

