Adverse Event Reporting		X	X	X
Dexcom G6 CGM and iPancreas usage training		X		
Examination of sensor site after removal (if applicable)			X	X

Hypoglycemia Treatment Guidelines**CBG < 70 mg/dl**

- Give 15 grams of oral carbohydrate.

- Repeat treatment every 15 minutes as needed to raise blood glucose ≥ 70 mg/dl.
 - o If CBG < 70 mg/dL occurs during pramlintide treatment visit:
 - Give 15 grams of oral carbohydrate.
 - Repeat treatment every 15 minutes with 15 grams oral carbohydrate as needed to raise blood glucose ≥ 70 mg/dl.
 - Repeat CBG checks every 15 minutes for 45 minutes to ensure glucose is persistently ≥ 70 mg/dl.

Presence of STUPOR, LOSS OF CONSCIOUSNESS, or SEIZURE

- Give 3 mg glucagon intranasal
- Verify that insulin and pramlintide are turned off.

Hyperglycemia Treatment Guidelines

If the sensed glucose is ≥ 300 mg/dl, the participant will be instructed to check their blood glucose and to check the Omnipod for malfunction. This would include checking for insulin leaks, making sure Omnipod is securely adhered to skin, and check for error messages on the phone running the algorithm.

If capillary blood glucose value is over 300 mg/dl for more than 2 hours or is ≥ 400 mg/dl at any time, the participant will be instructed to check serum ketones using the Abbott Precision Xtra meter and to change out the Omnipod. If serum ketones are over 0.6 mM, the participant will be instructed by study investigator to discuss proper management, including delivering a correction bolus. In addition, the participant will be encouraged to drink sugar-free liquids. If serum ketones are above 1.5 mM at any time, the study will be stopped and insulin will be administered as directed by the on call investigator.

Cleaning and Disinfecting

All devices will be cleaned and disinfected between participants. The smart phone, Polar watch and Omnipod PDMs are cleaned by study staff. Technicians who are disinfecting units will wash hands thoroughly and wear gloves. All items will undergo intermediate-level disinfection using Oxivir TB disposable wipes. The disinfectant will be applied and allowed to air dry. After disinfection, when the units are completely dry, they will be placed in a sealed bag labeled with participant information.

Stopping Rules

Individual study stopping rules

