Any adverse event (AE) and/or unanticipated problem (UP) will be reported to the investigator monitor immediately by one of the investigators. Hypo- and hyperglycemia will not be considered AEs unless participant has positive ketones or displays symptoms of hypoglycemia such as: loss of consciousness, slurred speech, hospitalization or EMS services called. One of the investigators will always be on-call during the closed-loop studies and will write up a description of the adverse event/unanticipated problem. All reportable new information (RNI) will be reported to the IRB within five calendar days after the PI learns of the event. RNI is any information that might meet the regulatory definition of an unanticipated problem involving risks to participants or others or serious or continuing noncompliance that might impact the criteria for IRB approval. The report will be submitted to the IRB by the principal investigator or study coordinator. A summary of all UP's and adverse events, including those that do not meet the requirement for RNI, will be submitted with the continuing review. The FDA will be notified of any unanticipated adverse event related to the use of the study device. Notification will be made within 10 days after the Principal Investigator becomes aware of the event.

Confidentiality Procedures:

To protect confidentiality, standard institutional practices will be followed as described in the OHSU Information Security and Research Data Resource Guide (<http://ozone.ohsu.edu/cc/sec/isg/ressec.pdf>) to maintain the confidentiality and security of data collected in this study. Study staff will be trained regarding these procedures. See IRB protocol 19858 for a complete description of the confidentiality and security of the study data collected during this study to be stored in the OregonAPC repository.

Data for this project will be stored in an AWS server developed by our group that has undergone a security review.

Paper files will be stored in locked filing cabinets in restricted access offices at OHSU. After the study, source documents will be maintained at the participating clinical center (or offsite record storage facilities) 2 years after a marketing application is approved for our group's decision support device or discontinuance of pursuit of marketing approval.

[figure not shown]
Electronic data will be stored on encrypted: computers, laptops and study smartphones.

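### A capillary glucose of 301–399 mg/dL lasting 2 hours or less can stop the visit before lunch, or be present at discharge, with no required ketone test

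*Combined protocol and SAP*

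**What the plan says.** **On arrival.** Both treatment visits carry the same rule: "CBG values > 300 mg/dl will be managed at the discretion of the investigator with a correction bolus and serum ketones will be checked". The result then decides whether the visit begins: "If serum ketones are >0.6 mM, the study will not be started and insulin therapy will be guided by the onsite investigator".

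**After the start.** The Hyperglycemia Treatment Guidelines set a narrower trigger. A ketone test is required "If capillary blood glucose value is over 300 mg/dl for more than 2 hours", or as soon as it reaches 400 mg/dL. A sensor value of 300 mg/dL or more prompts a fingerstick and a pod check, but no ketone test.

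**Before lunch.** Meal Description, in both visits: "If CBG >300mg/dL before the lunch meal, then the study will be stopped early". The text that follows covers an insulin dose calculated by the investigator and an inspection of the pod site. It does not mention ketones.

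**At discharge.** A CBG above 180 mg/dL leads to a correction bolus reviewed with the investigator. The participant may then leave if the next "measurement 30 minutes later is less than 300 mg/dL or if the CGM glucose trend arrow shows flat arrow" or a downward arrow. The pramlintide visit uses the same rule when the first CBG is above 85 mg/dL. For a low first value on that visit the rule is stricter: glucose must recover to at least 85 mg/dL "and the CGM trend arrow is flat or trending up, then patient can be discharged".

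**Adverse events.** Monitoring Procedures: "Hypo- and hyperglycemia will not be considered AEs unless participant has positive ketones or displays symptoms of hypoglycemia". No ketone value is attached to the word positive.

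**General statement.** The risk paragraph under RISKS and BENEFITS says that glucose and ketones will be sampled frequently in all studies. It gives no time point or trigger, and Table 1 has no row for ketones.

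**The concern.** The plan requires a ketone test before it exposes a participant at more than 300 mg/dL to the closed loop. It requires none before it releases a participant at the same value, unless the elevation has lasted over 2 hours or reached 400 mg/dL. The two moments without a required test are those at which study staff hand care back to the participant.

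At stake is the detection of ketones that have already accumulated. Continued pod failure is not the worry, because the pod is removed and home insulin is restarted.

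Adverse events are a listed safety endpoint, and hyperglycemia in practice becomes one through a positive ketone result. If nobody tests, an asymptomatic ketosis is neither seen nor counted. If somebody does test, the result has no stated limit to be judged against.

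**Working it through.** No figure in the plan needs to be reproduced here. The check is to apply the written rules to the same glucose values.

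**Rules used**

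1. Arrival (both treatment visits): test ketones if CBG > 300 mg/dL, with no duration condition.
2. After the start (Hyperglycemia Treatment Guidelines): test if CBG > 300 mg/dL for > 2 h, or if CBG ≥ 400 mg/dL.
3. Pre-lunch stop (Meal Description, both visits): stop if CBG > 300 mg/dL; no test attached.
4. Discharge (both visits): release if the 30-minute CBG is < 300 mg/dL or the arrow is flat or down; no test attached.

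**Result**

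| CBG (mg/dL) | Duration | Test required on arrival | Test required after start | Stopped before lunch | Discharge on a flat arrow |
|---|---|---|---|---|---|
| 290 | 0.5, 2 or 2.5 h | no | no | no | allowed |
| 301, 350, 399 | 0.5 or 2 h | yes | **no** | yes | allowed |
| 301, 350, 399 | 2.5 h | yes | yes | yes | allowed |
| 400 | 0.5, 2 or 2.5 h | yes | yes | yes | allowed |

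The second row is the gap: 301–399 mg/dL for 2 h or less. Longer or higher excursions are tested under rule 2, which also covers the hours before lunch.

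**What the arrow alternative admits.** The protocol treats an arrow as flat when glucose changes by less than 1 mg/dL per minute in either direction. Over 30 minutes that allows a rise of just under 30 × 1 = 30 mg/dL. A down arrow means a fall of more than 30 mg/dL in 30 minutes, that is, more than 30/30 = 1 mg/dL per minute. Neither arrow comes with a glucose ceiling. Because the two conditions are joined by *or*, a 30-minute CBG above 300 mg/dL does not prevent release when the arrow is flat or down. It does when the arrow points up.

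**Later contact.** After the pramlintide visit, staff telephone about 1 hour after discharge and the participant takes a fingerstick. No such call is written for the insulin-only visit. The call measures glucose, not ketones.

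**Ketone limits in the plan.** 0.6 mM blocks the start on arrival and prompts management during the visit ("If serum ketones are over 0.6 mM, the participant will be instructed by study investigator to discuss proper management"). 1.5 mM stops the study and appears in the definition of ketoacidosis. Neither is linked to the adverse-event rule.

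**The case against.** The strongest defence is that the arrival test and the in-visit trigger serve different purposes. The arrival test is a gate after an unsupervised night. During the visit, sensor data arrive every 5 minutes, insulin delivery is known, staff are nearby and an investigator is on call. Meals are eaten without a pre-meal bolus, and the automatic bolus is cut by 25%, so high post-meal values are foreseeable. A trigger based on duration is then reasonable, and the untested excursions are the shorter and lower ones. The stricter low-glucose rule on the pramlintide visit can likewise be defended, since hypoglycemia is the more immediate risk on leaving. All of this stands as a reason not to test at every reading above 300 mg/dL. It does not explain omitting the test when the visit is abandoned for that value, or when the participant goes home with it.

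The promise of frequent ketone sampling is a real commitment, and the investigator may order a test at any time. But the promise has no schedule or trigger, so it does not make a test mandatory at either point. The plan chose not to leave the matter to discretion on arrival, where an investigator also manages the case.

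A reader might infer that the discharge rule sends people home on a course to 400 mg/dL. For example, 340 mg/dL rising at 0.9 mg/dL per minute would reach 400 in (400 − 340)/0.9 = 67 minutes. The documents do not support that projection. It ignores both the correction bolus and the restarted home insulin. The rule permits release with a slow rise; nothing shows that the rise would continue.

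**Conclusion.** The gap is real and narrow. Between 301 and 399 mg/dL for 2 hours or less, the plan requires no ketone test at the pre-lunch stop or at discharge, and this is so in both arms. What could be lost is asymptomatic ketosis, which would go undetected unless someone chose to test and so would not be counted as an adverse event.

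The size in visits cannot be given. The design has 35 × 2 = 70 planned visits, but the documents report no rate of such events, and none is assumed here.

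It would be wrong to conclude that the plan ignores ketones or would miss ketoacidosis. Sustained or higher glucose is tested, symptomatic ketosis can still be reported through its symptoms, and ketoacidosis halts the whole study. The hyperglycemia itself still enters the sensor endpoints and the count of provider-given insulin injections. Sample size, primary endpoints and analysis are unaffected.

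This is a desirable safety improvement, not a flaw that threatens the trial. It rests on the stop and discharge rules; the undefined term for positive ketones is supporting detail and would not justify the point alone.

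**What to change.** 1. **Meal Description, both visits.** When the visit is stopped because CBG exceeds 300 mg/dL before lunch, require a serum ketone check at that time.
2. **Discharge from inpatient clinic, both visits.** If the discharge CBG or its 30-minute repeat exceeds 300 mg/dL, require a serum ketone check before release. If ketones exceed 0.6 mM, the investigator directs insulin treatment and ketones are rechecked at a set interval, for example 60 minutes. Release follows once they are 0.6 mM or lower; a value above 1.5 mM leads to referral for care. These steps should be written out here, because the Hyperglycemia Treatment Guidelines contain no recheck interval or release limit, and their pod change cannot apply once the pod is off.
3. **Monitoring Procedures.** As a supporting wording change, define positive ketones as serum ketones above 0.6 mM, the limit that the plan already uses on arrival and during the visit.

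The cost is one or a few strips per event on the ketone meter already in use, and an occasional delayed discharge. The edits touch five places: two meal sections, two discharge sections and the adverse-event rule.
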